11.1.1.2.2 Adverse events of special interest

Potential Hy's Law, defined as $\geq 3 \times \text{ULN}$ ALT or AST with coexisting $\geq 2 \times \text{ULN}$ total bilirubin in the absence of $\geq 2 \times \text{ULN}$ ALP, with no alternative explanation for the biochemical abnormality, must ALWAYS be reported to UCB as an AE of special interest (ie, without waiting for any additional etiologic investigations to have been concluded). Follow-up information should then be reported if an alternative etiology is identified during investigation and monitoring of the subject.

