11.2.1 Evaluation of PDILI

The PDILI IMP discontinuation criteria for this study are provided in [Section 6.3.1](#), with the accompanying required follow-up investigation and monitoring detailed below. All PDILI events must be reported as an AE and reported to the study site and Sponsor within 24 hours of learning of their occurrence. Any PDILI event that meets the criterion for potential Hy's Law must be reported as an AE of special interest (see [Section 11.1.1.2.2](#)), and, if applicable, also reported as an SAE (see [Section 11.1.1.2](#)).

Evaluation of PDILI consists of the diagnostic testing and continued monitoring included in [Table 11-3](#) (specific tests dependent on laboratory results and corresponding symptoms) and consultation with a local hepatologist (if applicable; discussed in [Section 11.2.1.1](#)). The local hepatologist is the expert usually consulted by the treating physician for assessment and management of potential hepatic disease. This would usually be a hepatologist, but may be a gastroenterologist. Additional investigation and monitoring may be required and adapted based on the diagnosis after the cause of the liver injury/abnormality is confirmed (details in [Section 11.2.1.4](#)).

The results of all monitoring, including laboratory testing and other testing, should be made available to the study site and Sponsor.

All initial tests resulting in abnormal hepatic laboratory values need to be repeated, but appropriate medical action must not be delayed waiting for the repeat result.

If tests are done locally for more rapid results, a concurrent sample should also be sent to the central laboratory whenever possible. Medical care decisions are to be made initially using the most rapidly available results and a conservative approach must be taken if the results from the 2 laboratory tests are significantly different. Data from the local and central laboratory are to be recorded on the applicable eCRF pages.

When IMP is discontinued, all concomitant medications and herbal supplements that are not medically necessary should also be discontinued. In these cases, the Investigator should also consider dose reduction for medically necessary concomitant medication and consider changing any medically required concomitant medication known to be hepatotoxic to a suitable alternative.

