- ^a Hepatitis symptoms include fatigue, nausea, vomiting, and right upper quadrant pain or tenderness; hypersensitivity symptoms include eosinophilia (>5%), rash, and fever (without clear alternative cause).
- ^b If the subject also has $\geq 2 \times$ ULN ALP, the possibility of an indication of biliary obstruction should be discussed with the Medical Monitor.
- ^c Details provided in [Section 11.2.1.1](#). The local hepatologist is the expert usually consulted by the treating physician for assessment and management of potential hepatic disease. This would usually be a hepatologist, but may be a gastroenterologist.
- ^d Unless an alternative monitoring schedule is agreed by the Investigator and UCB Study Physician. Determination of stabilization is at the discretion of the Investigator in consultation with the hepatologist (as applicable) and UCB Study Physician, as needed.

REDACTED COPY
This document cannot be used to support any marketing authorization application and any extensions or variations thereof.

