### 10.3.1 Subjects with potential drug-induced liver injury (PDILI)

There are specific criteria described in the protocol Section 11 to evaluate subjects for potential drug-induced liver injury (PDILI). The evaluations required by protocol for PDILI subjects are collected on the following CRFs:

- Most Recent Study Medication Administration, for PDILI
- Laboratory Tests DILI
- Vital Signs DILI
- Hepatic Event Supplemental Medical History for PDILI
- Potential Hepato-Toxic Medications Inquiry for PDILI

- Symptoms of Hepatitis and Hypersensitivity for PDILI
- Lifestyle PDILI
- Family Medical History for PDILI

Listings will be prepared presenting subjects with PDILI data. A summary of number and percent of subjects meeting PDILI criteria (ALT, AST, total bilirubin, ALP, and presence of symptoms) during the Treatment Period (scheduled and unscheduled visits) will be provided following the UCB standard table shell for PDILI Data. Subjects who met these criteria will be listed.

ALT Criteria	AST Criteria	Total Bilirubin Criteria	ALP Criteria	Presence of Symptoms
≥3xULN	≥3xULN	≥2xULN	≥2xULN	NA
≥8xULN	≥8xULN	NA		NA
≥3xULN	≥3xULN	NA		Y
≥3xULN <-5xULN and ≥2x Baseline	≥3xULN <-5xULN and ≥2xBaseline	<2xULN		N
≥5xULN <-8xULN and ≥2x Baseline	≥5xULN <-8xULN and ≥2xBaseline	<2xULN		N
≥5xULN and ≥2xBaseline	≥5xULN and ≥2xBaseline	<2xULN		N

N=No; NA=Not Applicable; ULN= upper limit of normal; Y=Yes.

A summary table highlighting the potential cases of Hy's Law, within each treatment group will be presented. Hy's Law is defined as:

- AST ≥3xULN or ALT ≥3xULN and
- Total Bilirubin ≥2xULN

In order to meet the above criteria, a subject must experience the elevation in bilirubin and ALT or AST at the same visit. For example, a subject who experiences a ≥2 x ULN elevation of bilirubin at one visit and a 3 x ULN elevation in ALT (or AST) at a subsequent visit has not fulfilled the Hy's law criteria.

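### The SAP's Hy's Law definition leaves out the protocol's ALP and alternative-explanation conditions, so a subject with raised ALP could be tabulated as a potential case that the protocol would not count

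*SAP*

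**What the plan says.** Protocol 11.1.1.2.2 defines potential Hy's Law as ALT or AST ≥3xULN with coexisting bilirubin ≥2xULN, and then narrows it in two ways. The ALP condition reads "total bilirubin in the absence of $\geq 2 \times \text{ULN}$ ALP", and the second condition is "with no alternative explanation for the biochemical abnormality". An event of this kind "must ALWAYS be reported to UCB as an AE of special interest". Protocol 11.2.1 repeats the link: "Any PDILI event that meets the criterion for potential Hy's Law must be reported as an AE of special interest".

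SAP 10.3.1 says: "A summary table highlighting the potential cases of Hy's Law, within each treatment group will be presented". It then defines Hy's Law in two bullets: AST or ALT ≥3xULN, and total bilirubin ≥2xULN. The sentence after the bullets is about timing only: "In order to meet the above criteria, a subject must experience the elevation in bilirubin and ALT or AST at the same visit". ALP does not appear in this definition, and neither does the alternative-explanation condition.

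ALP does appear earlier in the same SAP section, in the separate PDILI summary. The first row of that criteria table, as it reads in the available text, sets ALP ≥2xULN beside ALT/AST ≥3xULN and bilirubin ≥2xULN. Subjects meeting the PDILI criteria are also to be listed. SAP 10.2 plans an incidence table for TEAEs of special interest. SAP 3.9 states that nothing has changed from the protocol-defined analyses.

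**The concern.** The protocol treats the ALP condition as meaningful. For the same transaminase and bilirubin pattern, footnote b of Protocol Table 11-3 says that if ALP is also ≥2xULN, "the possibility of an indication of biliary obstruction should be discussed with the Medical Monitor". A subject with that pattern is outside the protocol's definition of potential Hy's Law but inside the SAP's.

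The SAP rule has the same thresholds as one of the protocol's PDILI criteria for stopping IMP (Protocol 6.3.1), which carries no ALP exclusion. The protocol keeps that criterion and potential Hy's Law apart; the SAP table attaches the Hy's Law name to the broader one.

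What is at stake is how one small count is read. Potential Hy's Law is the only event in the protocol's section on AEs of special interest, and Protocol 11.1.1.2 gives it as an example of an important medical event. A reader of the table would take its rows to be cases as the protocol defines them, and nothing in the table would warn otherwise.

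**Working it through.** There is no sample size, power or event count to recompute. The check sets the two definitions side by side and applies each to the possible patterns.

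**Conditions**

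| Condition | Protocol 11.1.1.2.2 | SAP 10.3.1 Hy's Law table |
|---|---|---|
| ALT or AST ≥3xULN | required | required |
| Total bilirubin ≥2xULN | required | required |
| Timing | elevations coexist | same visit |
| ALP not ≥2xULN | required | not stated |
| No alternative explanation | required | not stated |

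**Patterns**

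| Pattern | SAP table | Protocol definition |
|---|---|---|
| (a) ALT/AST ≥3xULN and bilirubin ≥2xULN at the same visit, ALP <2xULN, no alternative explanation | counted | met |
| (b) As (a), but ALP ≥2xULN | counted | not met |
| (c) As (a), but with an alternative explanation | counted | not met |
| (d) ALT/AST and bilirubin elevations at different visits only | not counted | undetermined, because coexistence is not tied to a visit |

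**What follows**

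1. For same-visit elevations, every subject who meets the protocol definition also meets the SAP rule, and patterns (b) and (c) meet only the SAP rule. The SAP count is therefore equal to or greater than the protocol-defined count. The difference is the number of subjects in (b) or (c).
2. Pattern (b) can be separated from laboratory data. ALP is a planned chemistry parameter in SAP Table 10-1.
3. Pattern (c) cannot be separated from laboratory data, because it needs a medical judgement. The protocol also has the event reported before the search for another cause is complete, with follow-up if one is found, so an event first reported as of special interest may later be explained.
4. The documents give no rate for pattern (b) or (c), so the size of the difference cannot be estimated. As an illustration only: if no subject met the protocol definition and one subject had pattern (b), the table would show 1 where the protocol's definition gives 0.

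**The case against.** The best defence is that this table is a screen. It highlights potential cases, it loses no protocol-defined case with same-visit elevations, and its thresholds are ones the protocol itself uses for PDILI. Screening broadly and then adjudicating from listings is a defensible approach. That stands as a reason to keep the row. It does not justify presenting the row as the definition of Hy's Law when the protocol's definition is narrower.

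Second, ALP is not ignored. The PDILI summary in the same section carries an ALP ≥2xULN criterion at these thresholds, and subjects meeting the criteria are listed, so a careful reader could find the raised-ALP subjects by cross-reference. This reduces the harm but does not remove it. The Hy's Law table does not flag those subjects, the PDILI row states no same-visit rule, and no row isolates ALP <2xULN, which is the protocol's case.

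Third, Protocol 13.4.1 plans no Hy's Law table, so it can be said that no protocol-defined analysis has been altered and that SAP 3.9 is literally true. That is fair for the analysis. The definition is the protocol's, however, and the SAP departs from it without saying so.

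A reader might also infer that the report will contain two conflicting counts under one name, one here and one in the table of TEAEs of special interest. The documents do not support that. The SAP 10.2 table is not titled Hy's Law. It counts reported adverse events, whereas this table counts laboratory values, and the two can differ for reasons unrelated to ALP.

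**Conclusion.** The point holds as a mismatch of definition and labelling in one descriptive safety table. The SAP's stated rule would classify a subject with ALP ≥2xULN, or with an established alternative explanation, as a potential Hy's Law case against the protocol's own definition.

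The consequence is conditional: the count is affected only if such a subject occurs. A reader might infer that the Hy's Law figure will be inflated, but without a rate in the documents that cannot be said. The direction is known for same-visit elevations, where the error can only be over-inclusion. No hypothesis test uses this table and efficacy conclusions are untouched. This is a worthwhile correction of low severity.

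The conclusion assumes that the two bullets are the complete programming rule for the table, which is how SAP 10.3.1 presents them.

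**What to change.** In the Hy's Law table of SAP 10.3.1:

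- Add a row for ALT or AST ≥3xULN, total bilirubin ≥2xULN and ALP <2xULN at the same visit, labelled as the laboratory criteria of Protocol 11.1.1.2.2.
- Keep the existing row, relabelled as a broader biochemical screen without the ALP condition.
- Footnote that the absence of an alternative explanation is judged by medical review and is not derived from laboratory values. Adding ALP alone does not reproduce the full protocol definition, and the label should not suggest that it does.
- Reconcile the subjects in the new row with the reported AEs of special interest, and explain any differences.

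The cost is one row, one label, one footnote and a short reconciliation. ALP is already a planned laboratory measurement, so no new data are needed. The change concerns reporting only and leaves every clinical rule in the protocol as it is.

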## 10.4 Vital signs, physical findings, and other observations related to safety

### 10.4.1 Vital Signs

Vital measurements (including SBP, DBP, PR, RR and weight) are generally collected in standard units. If any measurements are collected in international units, they will be converted to standard units for summaries. Subject Listings will be prepared for vitals variables.

The observed value and change from Baseline will be summarized descriptively by treatment group and scheduled study visit. In the same table, the observed value and change from Baseline

will be summarized by treatment for all scheduled visits. The Last Visit, minimum, and maximum post-baseline values during the Treatment Period will also be included.

The number and percentages of subjects with abnormal vital signs and body weight during the Treatment Period will be presented by treatment group and PSL total group. The abnormal vital sign and body weight criteria are provided in Appendix 13.2. Subject numbers for those meeting abnormal criteria will also be presented.

#### **10.4.2 Electrocardiograms**

ECG parameters include heart rate, PR interval, QRS duration, QT interval, QTcB [QT corrected for heart rate using Bazett's formula], and QTcF [QT corrected for heart rate using Fridericia's formula].

The observed ECG parameter values and their change from Baseline will be summarized (SS) descriptively by treatment group and PSL total group for each scheduled assessment visit. The Last Visit, minimum, and maximum post-baseline values during the Treatment Period will also be included. In addition, the number and percentage of subjects with QTc (Bazett and Fridericia corrected) classifications of <450ms, 450 to <480ms, 480 to <500ms, and  $\geq$ 500ms and change from baseline of <30ms, 30 to <60ms, and  $\geq$ 60ms will be presented for each visit.

For each ECG, the overall ECG result, is also collected, categorized as one of: no abnormality, an abnormal but not clinically significant finding, or a clinically significant finding. The number and percentage of subjects with no abnormality, an abnormal but not clinically significant finding, and a clinically significant finding will be summarized for each of the scheduled assessment visits. Percentages for the visit will be relative to the number of subjects with an ECG result for the visit.

The number and percentages of subjects with abnormal ECG during the Treatment Period will be presented by treatment group and PSL total group. The abnormal ECG criteria are provided in Appendix 13.3. Subject numbers for those meeting abnormal criteria will also be presented.

#### **10.4.3 Echocardiograms**

Echocardiogram data are collected at Visit 1, Visit 6, and Visit 9. Depending on the availability of data, echocardiogram abnormalities (Left Ventricle, Left Atrium, Right Ventricle, Right Atrium, Pericardium, Pulmonary Artery Systolic Pressure and overall assessment) will be summarized by treatment group and PSL total group and scheduled visit as the number and percentage of subjects with an abnormality. In addition, Echocardiogram Valvular abnormality grade (Aortic Valve, Mitral Valve, Tricuspid Valve, Pulmonary Valve) described in Appendix 13.4 will be summarized descriptively. Valvular abnormality grade equal or larger than grade 2 is corresponding to valvular abnormal. Subject numbers with abnormality for any assessment will be provided.

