c Questionnaires to be completed by all subjects prior to any other study procedures at the visit, when possible.

d If an unscheduled visit is conducted due to safety or efficacy reasons, a C-SSRS assessment will be performed with the subject during the visit. If an unscheduled visit is conducted for reasons other than safety or efficacy concerns (eg, replacement of lost medication, repeated collection of a laboratory specimen due to collection, or analysis issues), a C-SSRS will not be required at these visits.

e Vital signs measured in supine position after 5 minutes of rest include pulse rate, respiratory rate, systolic BP, and diastolic BP.

f Height will only be measured at Visit 1.

g Full physical examinations will assess cardiac and respiratory function via auscultation and review of the following body systems: general appearance; ear, nose, and throat; eyes; hair and skin; respiratory; cardiovascular; gastrointestinal; musculoskeletal; hepatic; neurological; and mental status. Brief physical examinations will include a review of the following body systems: general appearance (including mental status); skin; respiratory; cardiovascular; gastrointestinal; and hepatic.

h Brief neurological examination will include a general assessment and evaluation of reflexes, muscle strength and coordination, and cerebellar function. Full neurological examinations will include in addition, evaluation of cranial nerves, motor system (general muscle strength and tone), sensations in upper/lower extremities.

i Baseline ECG has to be scheduled and results received before Visit 2. An ECG at the SFU Visit will be performed only if abnormal at end of treatment or premature discontinuation visit. All ECG recordings will be performed with the subject resting in the supine position for at least 5 minutes.

j The echocardiogram will be conducted at Visit 1. Echocardiograms will be repeated at Visit 6 for subjects continuing the OLE study. Subjects discontinuing will have an echocardiogram 30 days after last IMP intake at the SFU Visit (except if performed at Visit 6). A repeat echocardiogram will be performed for subjects with a new finding, Grade 2 (moderate severity), or Grade 3 (severe severity).

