k An echocardiogram will also be performed 6 months after last IMP intake for subjects exposed to >3 weeks to IMP and discontinuing the study (but not for subjects with <3 weeks exposure).

l AED samples will ideally be taken immediately prior to dose of concomitant medication on each occasion. If this is not possible, then the sample may be taken at any time after dose and the timing of sample in relation to dose should be kept the same ( $\pm 1$  hour) on each occasion for each subject. Therefore, the timing of visits for each subject when AED samples are collected should be scheduled approximately at the same time whenever possible. Assay of parent PSL and metabolites may be included in the AED panel of tests at Visits 6 and 7.

m On Visits 6 and 7, unless the concomitant AED sample is within  $\pm 5$  minutes of a scheduled MITRA sample for PSL assay, a separate, additional MITRA sample will be taken at same time as the concomitant AED blood sample.

n Subjects are requested to provide blood samples for measurement of PSL and metabolites whenever possible. On Visits 3, 5, and 6, site personnel should obtain blood samples for measurement of random PSL concentrations at any time between IMP intake and record accurately the time of last IMP intake and the time of sample collection. On Visits 4 and 7, blood samples for measurement of sparse PK profiles will be collected as follows: immediately before IMP intake

---

(maximum 15 minutes before intake) and then 3 times after (between 30 minutes and 3 hours after IMP intake), taken at least 30 minutes apart. All samples may be taken either at home or in the site or partly at home and partly at the site.

o For all female subjects, serum pregnancy test at Visits 1 and 7 (in case the subject enters into the OLE study) and where applicable, Urine pregnancy test will be used at other visits for female subjects of childbearing potential.

p Seizure counts are collected on the subject's daily record card on a daily basis.

[figure not shown]
q At each visit following an IMP dispensation, IMP should be presented to check for compliance.

r Subject entry interview will be performed on a voluntary basis either at Visit 1 or Visit 2. Subject/caregiver exit interview/survey will be performed on a voluntary basis either at Visit 6 or Visit 7.

s The SFU Visit will be performed only for subjects who do not enter EP0093.

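### No planned table pools post-Baseline echocardiogram findings into a treatment-emergent incidence per treatment group, and each by-visit row describes a subset selected after randomisation

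*SAP*

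**What the plan says.** SAP 10.4.3 opens with "Echocardiogram data are collected at Visit 1, Visit 6, and Visit 9". Chamber, pericardial, pulmonary-pressure and overall abnormalities "will be summarized by treatment group and PSL total group and scheduled visit as the number and percentage of subjects with an abnormality". Grades for the four valves "will be summarized descriptively. Valvular abnormality grade equal or larger than grade 2 is corresponding to valvular abnormal". The section ends with "Subject numbers with abnormality for any assessment will be provided".

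The schedule in SAP Table 2-1 (footnotes j and k) decides who is scanned when:

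- Visit 6: "Echocardiograms will be repeated at Visit 6 for subjects continuing the OLE study".
- Visit 9: "Subjects discontinuing will have an echocardiogram 30 days after last IMP intake at the SFU Visit (except if performed at Visit 6". Footnote s limits this visit to subjects who do not enter EP0093.
- Six months: "An echocardiogram will also be performed 6 months after last IMP intake for subjects exposed to" IMP for more than three weeks who then discontinue.

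Protocol Table 5-1, 8.4 and 11.3.3 carry the same Visit 6 exception. Protocol 5.1 and SAP 2.6.1 (Safety Follow-Up Period) ask for the 30-day echo in everyone not entering the OLE and do not mention the exception.

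Three general statements also bear on this. SAP 3.1 keeps unscheduled data out of by-visit summaries. SAP 3.2.5 adds a Last Visit row confined to the Treatment Period. Protocol 13.4.1 commits to describing echo results at Baseline, during treatment and after it, together with changes from Baseline.

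**The concern.** A subject normally has one scheduled post-Baseline echo, and the visit at which it falls depends on how treatment went. The Visit 6 row is a table of continuers and the Visit 9 row a table of those who stopped or declined the OLE. If continuation differs by dose, neither row compares like with like. The percentages are also prevalences: mild findings already present at Visit 1 are counted with new ones.

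Occurrence of valvular or pericardial change, read centrally, is a named safety variable (protocol 4.2.2). Valvular grade is a withdrawal criterion (protocol 6.3), and cardiac events are singled out for the DMC (protocol 13.7). The natural question is what fraction of each treatment group developed a new finding at any time after Baseline. No listed output answers it.

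**Working it through.** The plan states no figure for this point, so there is nothing to reproduce. The check is mainly a comparison of passages.

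**Step 1: where each echo would appear.**

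| Echo | Who has it | By-visit row | Last Visit row | Pooled per-subject table |
|---|---|---|---|---|
| Visit 6 | OLE continuers | yes | yes, by default | none planned |
| Visit 9 | those stopping without a Visit 6 echo | yes | no, after the Treatment Period | none planned |
| Unscheduled repeat, Treatment Period | new or worsening findings (protocol 6.3.2) | no | yes, by default | none planned |
| Unscheduled repeat, later | as above | no | no | none planned |
| 6-month | those stopping after more than 3 weeks of IMP | not named in 10.4.3 | no | none planned |

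**Step 2: does the closing sentence of 10.4.3 fill the gap?** SAP 10.4.2 uses similar words after an n (%) table has already been specified: "Subject numbers for those meeting abnormal criteria will also be presented". There they are an addition to the percentages, so they most likely mean subject identifiers. The echo sentence gives no denominator, though its wording is not conclusive.

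**Step 3: comparison with other safety data.** Laboratory, vital-sign and ECG data (SAP 10.3, 10.4.1, 10.4.2) each have an any-time n (%) for the Treatment Period. Echo data have none.

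**Step 4: protocol against SAP.** SAP 10.4.3 specifies no change or shift from Baseline, although protocol 13.4.1 promises one and SAP 3.9 declares no changes to the protocol's analyses.

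**Step 5: illustration.** Take 80 per arm (SAP 2.7). Let c be the share scanned at Visit 6 and 1−c the share scanned only at Visit 9, with abnormality rates p6 and p9. Pooled incidence = c·p6 + (1−c)·p9. The documents give none of c, p6 or p9; all are assumed.

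- For c from 0.5 to 0.9, an arm splits into 40 to 72 Visit 6 echoes and 40 to 8 Visit 9 echoes.
- With p6 = 2% and p9 = 15% in every group, c = 0.9 gives 0.9×0.02 + 0.1×0.15 = 3.3%, and c = 0.6 gives 0.6×0.02 + 0.4×0.15 = 7.2%. By-visit percentages are identical while pooled incidence differs.
- With c = 0.7 and four affected subjects split two and two, the rows read 2/56 = 3.6% and 2/24 = 8.3%. Adding them gives (2+2)/(56+24) = 4/80 = 5.0%.
- With no events, the one-sided 95% upper bound is 1 − 0.05^(1/n): 3.7% for n = 80, 4.6% for n = 64, 17.1% for n = 16 and 31.2% for n = 8. Clean rows in small subsets exclude much less than a clean pooled row.

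**The case against.** The strongest reply is that little is lost. The SAP plans counts as well as percentages, so if the Visit 6 and Visit 9 sets are disjoint a reader can add them, as in the last step of the working. That stands: for those two visits the pooled count is recoverable. It does not recover post-treatment unscheduled or 6-month findings, or separate new findings from those present at Visit 1.

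A reader might infer that echo abnormality is never tabulated by treatment group. The documents do not support that, since number and percentage by treatment group are planned. A reader might also infer that valve grades are tabulated only by visit. The valvular sentence is not tied to visit; equally, it specifies no worst grade, pooling or denominator.

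Other replies hold in part:

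- Protocol 13.4.1 already promises change from Baseline, and SAP 1 defers to the protocol unless otherwise specified. The commitment exists, but no output carries it out.
- Exclusion criterion 14 removes Grade 2 or higher at screening, so among eligible subjects a later Grade 2 valve finding is new. A shift table adds less at that threshold, but still informs on milder grades and non-valvular findings.
- Abnormal echoes fall within the AE definition, and TEAEs are tabulated by period, including taper and follow-up (SAP 10.2). This depends on investigator reporting and does not replace the central read.
- Worst-value summaries suit repeated measures, and most subjects have one scheduled post-Baseline echo. True, but repeat scans occur precisely where something was seen.
- Adding the 6-month echo to a worst-grade summary would give non-continuers an extra look. This is right, and the fix keeps that echo separate.

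**Conclusion.** The point holds as a gap in presentation, not as an error that undermines the safety analysis. The planned rows compare subsets formed after randomisation, on prevalence that includes Baseline findings. No named table gives any-post-Baseline, treatment-emergent incidence per treatment group. Post-treatment unscheduled and 6-month findings reach no percentage summary.

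It rests on the Visit 6 and Visit 9 sets being largely complementary, which most of the schedule text says but protocol 5.1 and SAP 2.6.1 do not. If some subjects have both echoes, simple addition would double-count them and a per-subject table would be needed even more.

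The size is unknown. The 3.3% and 7.2%, the 70% continuation and the two-and-two split are all assumptions. A reader might infer that the layout hides a known dose-related signal; nothing in the documents supports that. Nor is this a comparison by randomised arm, because the Safety Set is analysed by treatment actually administered (SAP 3.5.3 and 10). Efficacy and Type I error are unaffected.

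**What to change.** Add one Safety Set table to SAP 10.4.3, by treatment group (actual treatment) and PSL total. For each valve and overall, show the worst post-Baseline grade and any new abnormality relative to Visit 1, as a shift, across Visit 6, Visit 9 and unscheduled echoes. Use subjects with any post-Baseline echo as the denominator and state how many have none. Report the 6-month echo in a separate row, because only subjects not continuing have it. Keep the by-visit tables, and say whether the subject numbers promised at the end of 10.4.3 are identifiers or counts.

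Reconcile protocol 5.1 and SAP 2.6.1 (30-day echo, no exception) with protocol Table 5-1, 8.4 and 11.3.3 and SAP Table 2-1 (exception for a Visit 6 echo).

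The cost is one extra descriptive table from data already collected. Its denominator is still formed after randomisation, and it mixes on-drug with off-drug readings; a footnote should say so.
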